Healthy Hydration Pilot in Elementary Schools

NCT06132763

05/07/2025

D. POWER/ANALYSIS PLAN. Students, the unit of analysis, are nested within schools. Thus, we have a cluster RCT with 2 clusters (intervention and control school). To detect a 10% mean difference in water bottle usage between groups, with a common SD of 15, an unadjusted sample size of 17/group would be needed. Adjustments to this sample size were made using a variance inflation factor (based on the assumption of an ICC of .03) to accommodate homogeneity within the clusters. Using this assumption, 2 clusters of average size of 200 is sufficient to detect the hypothesized difference at $\alpha=.05$ (two-sided) and a desired power of 80%. Thus, our proposed sample will be more than adequate to evaluate study aims. Contingency tables and frequency distributions will be evaluated and descriptive and inferential statistical analysis applied. Differences between schools in % of students with water bottles, hydration station counts (per student), % of students with SSBs at lunch, and beverage intake (BEV-Q; SSB, water, milk) will be evaluated using chi-square analysis. Difference between baseline and post values on these study outcomes will indicate an intervention effect, with one-way ANOVA conducted to test group differences. We will also graphically examine monthly trends in hydration station usage by school. Paired t-tests will examine differences in these outcomes by school. We will also examine interrater reliabilities (Kappas) among dental assessors and report baseline and post body mass index (BMI, BMIz, BMI percentile) and dental caries status (ICDAS criteria), as well as any observed differences by school over time (although none are expected in this study duration) to inform methods applied in a future trial. Descriptive statistics will be applied to examine trial feasibility (e.g., recruitment, retention, satisfaction, and implementation). Triangulating all data sources will be the basis for deriving final conclusions and recommendations for our future intervention.

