Healthy Hydration Pilot in Elementary Schools

NCT06132763

05/07/2025

1. STUDY DESIGN AND METHODS. Our team recognizes the broader context that influences student hydration behavior. As such, the proposed research involves multiple components aligning with levels of the social-ecological framework to advance water equity. All schools in will have hydration stations and be operating under their model hydration policy in the 2022-23 school year. We will randomly select a pair of matched elementary schools for study inclusion. One school will serve as the Intervention school and the other as the Control. To test study aims, we will conduct a 2 (Intervention and Control) x 2 (baseline and post) cluster pilot RCT, with students nested within schools. Both schools will receive water bottles and Hydration Tip sheets. In the Intervention school, we will collaborate with student ambassadors and our Community Advisory Board (CAB) to develop hydration marketing materials. We will then pilot a 12-week intervention that includes a student-developed marketing campaign plus positive reinforcement of water bottle use in school. Teachers will receive state standards of learning-aligned lessons related to hydration. Assessments of hydration station usage will be conducted at baseline, weekly throughout the intervention, and 12-weeks (post). Beverage selection and water bottle use at lunch will be assessed at baseline, monthly throughout the intervention, and post. School personnel and 4th and 5th grade students will complete online surveys via REDCap at baseline and post. The primary aim is to determine intervention feasibility, evidenced by the ability to recruit and retain student ambassadors, implement the intervention components as planned, and ratings of school personnel satisfaction. Secondary outcomes of interest are 1) % of students with water bottles at lunch, 2) hydration station usage, and 3) sugar-sweetened beverage (SSB) selection at lunch. We will also test our protocols for assessing body mass index (BMI) and dental caries status with a subset of 3rd grade students. Although we do not anticipate change on these measures in this short duration, these will inform methods applied in a larger trial. To acknowledge the district's time and involvement in this study, each participating school will select an incentive valued up to \$500 that is related to an identified school need (e.g., kitchen, recess, or PE equipment).

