1.1 Target Population and Setting. The respective school district serves >26,000 students within 25 elementary schools (22 Title I and thus eligible for this study). Students identify as Black (56%), white (21%), Latinx (19%), multiracial (3%), and Asian (2%). The majority (>90%) of students participate in the NSLP and all students receive free meals. For the current study, all Title I elementary schools will first be categorized based on race (%Black) and ethnicity (%Hispanic); two matched schools will be randomly selected and assigned to either Intervention or Control group (methods successfully applied in our prior work in this district). Potentially eligible schools have a mean enrollment of 400 students (range 145-854); we anticipate obtaining lunchroom observations from >80% of students on each rating day, for a projected sample of ~320 student observations per day in each school. Numbers will change based on the population of the selected schools. A subset of 3rd graders who have active parent consent and student assent will complete biomedical assessments.

1.2. Student Ambassadors. We will work with a local non-profit that has successful health-related programming in the schools and the school district to solicit student ambassador nominations. Both student self- and teacher nominations will be accepted. Teachers will describe ambassador roles and responsibilities, which include determining incentives, developing marketing materials and assisting the teacher ambassador with recording hydration station usage from the device, and other intervention-related tasks as relevant. Interested students will complete an interest form, signed by their parent/guardian. Teachers will select 2-3 ambassadors. In these ways, this study will build capacity and partner with students, teachers, and the CAB to enhance study relevance. To maintain study rigor, we will train students and teacher liaisons on study procedures. Ambassadors will receive compensation for this work.

1.3. Marketing Design. In the Intervention school, student ambassadors and a graphic design consultant will attend 5 meetings to develop healthy hydration promotional materials. Meetings will be guided by Appreciative Inquiry (AI) an asset-based approach to engage participants in

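### With one school per arm, student-level chi-square and ANOVA cannot show an intervention effect; at the SAP's own ICC the lunchroom chi-square has a 46% to 55% false-positive rate

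*SAP*

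**What the plan says.** Protocol section 1 sets out a cluster pilot RCT in which "One school will serve as the Intervention school and the other as the Control". Section 1.1 says the pair is matched on racial and ethnic composition (%Black, %Hispanic) and gives the lunchroom data volume: "for a projected sample of ~320 student observations per day in each school". For the survey, section 1 says "School personnel and 4th and 5th grade students will complete online surveys via REDCap at baseline and post".

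SAP section D names the student as the unit of analysis and continues: "Thus, we have a cluster RCT with 2 clusters (intervention and control school". Clustering enters the sample size through a variance inflation factor, "based on the assumption of an ICC of .03) to accommodate homogeneity within the clusters". It does not enter the analysis:

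- Between-school differences in water bottles, station counts, sugar-sweetened beverages (SSBs) and reported intake are tested without a stated cluster adjustment; the list ends "beverage intake (BEV-Q; SSB, water, milk) will be evaluated using chi-square analysis".
- On change over time: "Difference between baseline and post values on these study outcomes will indicate an intervention effect", "with one-way ANOVA conducted to test group differences".
- Paired t-tests by school are added.

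Neither document gives a mixed model, GEE, design-effect correction or cluster-level analysis, or a caveat about having one school per arm. The SAP instead calls its sample more than adequate. Feasibility, the primary aim, is to be described only.

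**The concern.** The SAP accepts that pupils in one school resemble each other, then tests them as if they did not. That inconsistency alone would inflate the type I error. The deeper problem is identification. With one school per arm, school and arm are the same variable in the chi-square, and school-by-time and arm are the same variable in the ANOVA on change. Adding a random school effect does not help, because the data hold no information on how much schools vary within an arm.

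Followed as written, a significant result on water bottles or SSB selection would be credited to the intervention when it may only show that two schools differ, or drifted differently over 12 weeks. The SAP draws its conclusions and its advice for the later intervention from all data sources together, so the misreading would carry into the next trial.

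**Working it through.** **Inputs.** SAP section D: ICC .03, average cluster size 200, two-sided alpha .05, power 80%, difference 10, SD 15, 17 per group before inflation. Protocol section 1.1: about 320 lunchroom observations per school per day, mean enrollment 400 (range 145 to 854), more than 80% observed.

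**The plan's own figure.** The two-sample formula gives 2 × [15 × (1.960 + 0.842)/10]² = 35.3, so 36 per group, not 17. The one-sample or paired form gives 17.66, close to 17. At m = 200 the inflation factor is 1 + 199 × .03 = 6.97, and 17 × 6.97 = 118.5, below 200. The sizing therefore applies a design effect of about 7 that the analysis omits. The 17 versus 36 discrepancy is a separate matter and is not needed here.

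**Degrees of freedom.** Two schools in two arms leave 2 − 2 = 0 degrees of freedom for between-school variance within arm. A re-randomisation test has two possible allocations, so its smallest p-value is 0.5 one-sided and 1.0 two-sided.

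**Chi-square between schools.** If the intervention does nothing, the unadjusted statistic is too variable by VIF = 1 + (m − 1) × ICC, and the true two-sided type I error is 2 × [1 − Φ(1.96/√VIF)].

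| m per school | ICC | VIF | True type I error |
|---|---|---|---|
| 200 | .03 (SAP) | 6.97 | 45.8% |
| 320 | .03 (SAP) | 10.57 | 54.7% |
| 200 | .01 (assumed) | 2.99 | 25.7% |
| 320 | .01 (assumed) | 4.19 | 33.8% |
| 114 | .03 | 4.39 | 35.0% |
| 114 | .01 (assumed) | 2.13 | 17.9% |

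The last two rows are for a survey outcome in grades 4 and 5. They assume 400 pupils spread equally over seven grades (400 × 2/7 ≈ 114), full response, and BEV-Q collected in the survey.

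Beta-binomial simulation of the Pearson chi-square at ICC .03, with assumed prevalences from .1 to .5, gives 45.0% to 46.8% at m = 200 and 54.8% to 55.7% at m = 320. Across the enrollment range at ICC .03 the formula gives 35% at 116 observations (80% of 145) and 67% at 683 (80% of 854).

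**ANOVA on change.** Stable school differences cancel, so the ICC that matters is that of the change score, which the documents do not give. The same formula with assumed values gives:

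| Change ICC (assumed) | m = 200 | m = 320 |
|---|---|---|
| 0 | 5% | 5% |
| .001 | 7% | 9% |
| .005 | 17% | 22% |
| .01 | 26% | 34% |

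Simulated F-tests agree with these to rounding. A second route keeps ICC .03 at each time point and assumes a baseline-to-post correlation of the school effects, with a student-level correlation of 0 or .5. It gives 12% to 26% at a school-effect correlation of .9, 47% to 67% at 0, and 5% only when school effects are perfectly stable.

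No rate is given for station counts, which are read from a device, or for the paired t-tests. The latter appear to compare time points within a school, and they cannot attribute a change to the intervention either.

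**The case against.** The strongest reply is that the large figure belongs to a test the SAP does not itself label as the effect test. Chi-square is assigned to differences between schools; the claim of an intervention effect is attached to the baseline-to-post change. Read literally, a chi-square that rejects because two schools really differ is a correct answer. This is fair: 46% to 55% is a false-positive rate only if the result is read as evidence for the intervention. For the ANOVA, the inflation is unknown and could be slight.

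Other points stand in part:

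- **School size and ICC.** The .03 was stated for water bottle use, the schools are matched, and their size is not yet known, so the rate could be lower or higher. A Yates correction, which the SAP does not name, brings the simulated rates to about 41% to 45% (m = 200) and 52% to 54% (m = 320).
- **Linkage.** The ANOVA figures need one change score per student. Neither document says lunchroom observations are linked across days, although the student-level unit and the paired t-tests imply it.
- **Pilot status.** The primary aim is feasibility, and conclusions draw on several sources rather than one p-value.

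None of this removes the aliasing, which holds at any ICC, any school size and for either test. Pilot status would excuse a descriptive plan, but this plan is powered for a group difference and names the result an effect.

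**Conclusion.** The concern holds and must be fixed. No p-value from this trial's data alone can separate the intervention from the school; one computed with an ICC imported from outside would rest wholly on that assumption. For a lunchroom outcome, the planned chi-square read as an efficacy test has a true error rate of 46% to 55% at the SAP's own ICC and the documents' cluster sizes of 200 and 320. The ANOVA on change is the test the SAP ties to an effect. Its rate is at least the nominal 5% and cannot be fixed more closely without a change ICC. The damage is confined to the secondary behavioural outcomes.

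**What to change.** In SAP section D:

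1. Remove between-school p-values as evidence of efficacy, and delete the statement that the baseline-to-post difference will indicate an intervention effect.
2. Put in its place wording such as: *For each outcome we will report baseline, post and change values for each school and the difference in change, descriptively. With one school per arm, the intervention cannot be separated from school differences.*
3. If intervals are shown, label them a sensitivity display and not calibrated 95% intervals. Multiply the standard error by √(1 + (m − 1) × ICC), using each outcome's own m and a stated range of assumed ICCs. At ICC .03 the multiplier is √6.97 = 2.64 for m = 200 and √10.57 = 3.25 for m = 320. For change scores use the ICC of change and include small values (0, .001, .005, .01).
4. Restate the 80% power claim and the sentence calling the sample more than adequate, so that the SAP is not powered for a test it no longer makes.
5. State that behavioural outcomes inform the future trial descriptively only.

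The cost is SAP wording. Data collection and the feasibility aim do not change. The sponsor gives up nominal efficacy p-values and shows wider uncertainty. Testing efficacy would instead require more schools per arm and a cluster-level or mixed-model analysis.

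### The power statement uses an SD of 15 for a yes/no outcome whose SD cannot be below 21.2 points; at the SAP's ICC, one-time power for 10 points is about 43% to 12%, not 80%

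*SAP*

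**What the plan says.** SAP section D sets the unit in its first sentence: "Students, the unit of analysis, are nested within schools". It then gives the basis for sample size: "To detect a 10% mean difference in water bottle usage between groups, with a common SD of 15", from which "an unadjusted sample size of 17/group would be needed". After inflation for an ICC of .03, it states that "2 clusters of average size of 200 is sufficient to detect the hypothesized difference" at two-sided alpha .05 and 80% power, and draws the conclusion "Thus, our proposed sample will be more than adequate to evaluate study aims".

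The analysis it names for this outcome is "Differences between schools in % of students with water bottles", which, with the other outcomes in that list, "will be evaluated using chi-square analysis". It adds a second analysis: "Difference between baseline and post values on these study outcomes will indicate an intervention effect, with one-way ANOVA conducted to test group differences".

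Protocol section 1 lists the share of students with a bottle at lunch as the first secondary outcome and says both schools are given bottles. Protocol section 1.1 projects about 320 student observations per school on each rating day. Neither document gives a baseline rate, a source for the SD of 15, or a per-student score for bottle use.

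**The concern.** An SD of 15 points suits a continuous score. The quantity described is a count of students with and without a bottle, compared by chi-square. For such data the SD is not free to be assumed: it equals the square root of p(1-p). An SD that is too small makes the required sample look too small.

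This is the only power statement in the SAP, and it supports a general claim of adequacy. The results are meant to inform a future intervention, and bottle use could be misread in either direction. A null result may reflect only low power once clustering is allowed for. A significant one may be a false positive, because the chi-square names no adjustment for clustering and one school per arm leaves the school effect inseparable from the treatment effect.

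**Working it through.** **Inputs.** From SAP section D: difference 10 points, SD 15, ICC .03, one school per arm, 200 students per school, two-sided alpha .05, power 80%. From protocol section 1.1: about 320 observations per school per rating day. The control rate is not given, so a range is assumed.

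**1. The SAP's own figure.** For two groups, n = 2 × [(1.96 + 0.84) × 15/10]² = 35.3, so 36 per group. Without the factor 2 the result is 17.7, close to the stated 17, but that is the one-sample or paired formula. With 17 per group, two-sample power is 49%.

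**2. Clustering, keeping SD 15.** The inflation factor is 1 + (m − 1) × .03.
- m = 200: factor 6.97, effective n = 200/6.97 = 28.7 per arm, power 71%.
- m = 320: factor 10.57, effective n = 320/10.57 = 30.3 per arm, power 74%.
- As m grows, effective n approaches 1/.03 = 33.3, which is below 36, so power cannot pass 78%.

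A possible explanation for the claim that 200 suffices is 17 × 6.97 = 118, which is below 200; the correct 36 × 6.97 = 251 is not. This is inference; the SAP does not show the step.

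**3. The SD of a yes/no outcome.** Pooled SD = √[(p₀q₀ + p₁q₁)/2], with q = 1 − p. Over all pairs 10 points apart the minimum is 21.2 points, at 0 vs 10% (or 90 vs 100%).

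**4. One-time power for 10 points.** Power = Φ(0.10/√[(p₀q₀ + p₁q₁)/n_eff] − 1.96), plus the negligible lower tail, with the ICC taken as known.

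| Rates | Pooled SD | 200 per school | 320 per school | Ceiling, any size |
|---|---|---|---|---|
| 0 vs 10% | 21.2 | 43% | 45% | 49% |
| 5 vs 15% | 29.6 | 25% | 26% | 28% |
| 10 vs 20% | 35.4 | 19% | 20% | 21% |
| 20 vs 30% | 43.0 | 14% | 15% | 16% |
| 40 vs 50% | 49.5 | 12% | 12% | 13% |

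Rates of 70 vs 80% give the same values as 20 vs 30%.

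**5. Sensitivity.**
- *ICC.* At 200 per school, the same five rows give 78, 50, 37, 27 and 22% at ICC .01, and 30, 18, 14, 11 and 9% at ICC .05. At ICC .01 and 320 per school, the 0 vs 10% row alone passes 80% (83%).
- *Formula.* An arcsine formula gives 68% to 75% at 0 vs 10% (from 200 per school to the ceiling), falls below 50% by 1 vs 11%, and agrees within 1 point from 5 vs 15%.

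**6. Change from baseline, by assumption only.** Take a flat control rate, an intervention rate rising 10 points from 5, 10 or 40%, and 320 per school. With m per school, T = .03 + .97/m and v = p(1 − p), the variance of a school's change is v₀T + v₁T − 2√(v₀v₁)(.03r + .97s/m), summed over the two schools. Here r is the school-level and s the student-level correlation over time.
- s = 0 (students not linked): power is 9% to 19% at r = 0, 26% to 58% at r = .9, and 45% to 76% at r = 1.
- s = .5 and r = 1: power is 74% to 90%.

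The documents give neither correlation.

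**7. The chi-square without adjustment.** Under a true null with ICC .03 it rejects with probability 2 × [1 − Φ(1.96/√factor)]: 46% at 200 per school and 55% at 320.

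**The case against.** The strongest objection is that the SAP takes the baseline-to-post difference as the sign of an intervention effect, so a one-time comparison is not the contrast that matters. This stands in part. The 43% to 12% range does not refute 80% for change, and step 6 shows that favourable correlations can exceed it. But the power sentence speaks of a difference between groups and gives no change-score SD or correlation, so it does not support 80% for change either.

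Second, the words about a mean difference and a common SD suggest a continuous measure. A per-student average over several rating days would have a smaller SD than a single yes/no. The documents define no such score, and they name a share of students tested by chi-square. Even if SD 15 were right, power would be 71%.

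Third, 43% at 0 vs 10% is a boundary case that the normal approximation handles badly. With 29 per arm, exact enumeration gives 33% for an uncorrected chi-square and 6% for Fisher's test, against 68% from the arcsine formula at 28.7. A rate of 0% is also unlikely when both schools receive bottles. This is fair: 25% to 12% (5 vs 15% to 40 vs 50%) is the more realistic span. It does not rescue the claim.

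Fourth, the planned chi-square as named would have nominal power of 52% to 99.7% at 200 per school. That power comes from ignoring the ICC the SAP itself assumes, at the false-positive rates in step 7.

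Last, this is a feasibility pilot whose conclusions draw on all data sources. That limits the severity but does not make the stated figure correct.

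**Conclusion.** The concern holds. SD 15 is impossible for one yes/no observation per student when the rates differ by 10 points. At ICC .03, one-time power is 43% to 12% at 200 per school, with a ceiling of 49% to 13% at any size by the normal approximation. Separately, and with no assumption about outcome type, the SAP's own inputs require 36 per group rather than 17 and give 71% power, never more than 78%.

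The power range rests on one yes/no value per student, one school per arm, a known ICC of .03 and an assumed control rate. Two schools cannot verify the ICC. Power for change remains undetermined. Bottle use is a secondary outcome, so this should be fixed but does not touch the primary feasibility aim.

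**What to change.** In SAP section D, replace the SD-15 calculation and the 80% claim with a two-proportion calculation at stated control rates and ICC .03. For about 320 observations per school, report either the one-time detectable difference at 80% power or the expected 95% half-width, 1.96 × √[2p(1 − p)/30.3]:

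| Assumed control rate | Detectable difference | 95% half-width |
|---|---|---|
| 10% | about 29 points | about 15 points |
| 30% | about 34 points | about 23 points |
| 50% | about 32 points | about 25 points |
| 70% | about 26 points | about 23 points |

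Using the pooled null variance adds about 1 to 2 points to the detectable differences.

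State beside the table that:
- the ICC is treated as known;
- two clusters can neither estimate it nor separate the school effect from the treatment effect;
- power for change depends on correlations that have not been specified.

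Withdraw the adequacy claim, and say that neither a null nor a significant bottle-use result is by itself reliable evidence for planning the larger trial. If a continuous per-student score was intended, define it and give the source of its SD; the factor of 2 still needs correcting.

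The cost is SAP wording only, with no change to enrolment or data collection. The stated figure becomes less favourable.

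### The planning figure of 17 per group should be 36 on the SAP's own inputs; with ICC .03 and one school per arm, 80% power is not reached at 200 per school or at any school size.

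*SAP*

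**What the plan says.** All the planning inputs are in SAP section D (Power/Analysis Plan). The target is set out as "To detect a 10% mean difference in water bottle usage between groups", and the SAP continues: "with a common SD of 15, an unadjusted sample size of 17/group would be needed". It then applies a variance inflation factor with an assumed ICC of .03 and concludes that "2 clusters of average size of 200 is sufficient to detect the hypothesized difference at" the two-sided 5% level with 80% power. The next sentence draws the inference: "Thus, our proposed sample will be more than adequate to evaluate study aims".

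The two clusters are the whole trial. Protocol section 1 says: "One school will serve as the Intervention school and the other as the Control". Protocol section 1.1 gives a mean enrolment of 400 in eligible schools (range 145 to 854) and projects about 320 observations per rating day in each school. Neither document mentions a baseline covariate, a baseline–post correlation or any other adjustment that would reduce the variance used for sizing.

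**The concern.** A difference of 10 with an SD of 15 is two-thirds of a standard deviation. Seventeen per group looks far too few for 80% power in a comparison of two independent groups; it is close to the size for a single sample. If the starting figure is about half what it should be, the cluster adjustment built on it is also too small.

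With one school per arm this can change the answer in kind, because adding students to a single school raises its effective sample only up to a ceiling. The check is therefore whether the correct requirement lies below or above that ceiling.

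At stake is the SAP's assurance that the sample can evaluate the study aims. The SAP plans inferential tests between schools. A reader who trusts the assurance could take a non-significant result as evidence of no effect. The protocol also says the pilot will inform a larger trial, and a sample size calculation carried forward from here would start from about half the required number.

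**Working it through.** **Inputs.** From SAP section D: difference 10, common SD 15, alpha .05 two-sided, power 80%, ICC .03, 200 students per school, one school per arm. From protocol section 1.1: about 320 observations per school per day; enrolment mean 400, range 145 to 854.

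**Step 1. Trying to reproduce 17 per group.**
- Two-sample z formula: n = 2 × (1.960 + 0.842)² × (15/10)² = 2 × 7.849 × 2.25 = 35.3, so 36. The t-based value is 36.3, so 37.
- Same formula without the factor of 2 (the one-sample or paired form): 7.849 × 2.25 = 17.66, which rounds up to 18. The t-based one-sample size is 19.7, so 20.
- Two-sample, one-sided: 27.8, so 28 (t-based 29).
- Two-sample t-test with a standardised difference of 1.0: 16.7, so 17. The SAP's standardised difference is 10/15 = 0.667.

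No two-sample calculation on the stated inputs gives 17. The missing factor of 2 is a plausible source, but the SAP does not show its working.

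**Step 2. Power at 17 independent students per group.** Power = Φ(0.667 × √(17/2) − 1.960) = Φ(−0.016) = 49%. The t-based value is 47%.

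**Step 3. Cluster adjustment at 200 per school.** The variance inflation factor is 1 + 199 × .03 = 6.97.
- From 17: 17 × 6.97 = 118, which fits within 200. On that figure the sample looks comfortable.
- From 35.3: 35.3 × 6.97 = 246, which does not fit within 200.

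**Step 4. Power by school size.** Effective n per arm = m / (1 + (m − 1) × .03). Power = Φ(0.667 × √(effective n / 2) − 1.960).

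| Students per school, m | Inflation factor | Effective n per arm | Power (z) | Power (t) |
|---|---|---|---|---|
| 145 (smallest eligible school) | 5.32 | 27.3 | 69% | 68% |
| 200 (SAP) | 6.97 | 28.7 | 71% | 70% |
| 320 (projected observations) | 10.57 | 30.3 | 74% | 72% |
| 400 (mean enrolment) | 12.97 | 30.8 | 74% | 73% |
| 854 (largest eligible school) | 26.59 | 32.1 | 76% | 75% |
| no upper limit | – | 33.3 | 78% | 76% |

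**Step 5. Why more students cannot help.** As m grows, effective n tends to 1/.03 = 33.3. The requirement is 35.3. Equivalently, 35.3 × .03 = 1.06 exceeds 1, so no m solves the sample size equation.

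**Step 6. Detectable difference at 80% power.** 2.802 × 15 × √(2 / effective n) gives 11.1 points at m = 200 and 10.8 points at m = 320.

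**Step 7. Sensitivity to the assumptions.** At m = 200, 80% power needs an inflation factor of at most 200/35.32 = 5.66, so an ICC of at most (5.66 − 1)/199 = .023. With the ICC held at .03, it needs an SD of at most about 13.5. For 80% to be reachable at any school size, the ICC must be below 1/35.32 = .028.

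**Step 8. What the formula leaves out.** It treats the ICC as known. With two schools and two arms, the degrees of freedom for between-school variance are 2 − 2 = 0, so the data cannot separate a school effect from an intervention effect. The powers above are therefore optimistic.

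**The case against.** The arithmetic is hard to dispute, but five points can be made against the weight placed on it.

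*The inputs may not suit the outcome.* Water bottle use is recorded per student, and the planned test is chi-square. If the outcome is yes/no, an SD of 15 points requires a proportion near 2% or 98%, since √(.023 × .977) = .15. Writing 36 would then repeat an SD that does not fit. This point stands, and it limits what 36 means: it is the size under the SAP's stated SD. It does not rescue the power claim, because a larger SD lowers power further. The documents give no baseline rate, but as an illustration a 10-point difference needs 199 per group before inflation for 10% versus 20%, and 392 for 45% versus 55%.

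*The ceiling is a near miss.* At 77.7% against 80%, it depends on an ICC of .03 and disappears below about .028. That is correct, but .03 is the SAP's own value. At its stated 200 per school the shortfall is 9 points, and the error of 17 against 36 does not involve the ICC.

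*The practical loss is modest.* The detectable difference moves from 10 to about 11 points. This is fair on the SAP's model, which leaves out the missing degrees of freedom.

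*Another reading could rescue it.* Two schools per arm would give 95% power at 200 per school, and a one-sided test 81%. The SAP specifies a two-sided test, and both documents describe one school per arm.

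*It is a feasibility pilot.* The primary aim is analysed descriptively and does not rest on this calculation. That stands. However, the SAP extends its adequacy statement to the study aims and plans inferential tests. That the calculation would be reused for the larger trial is a risk; the documents do not say it will be.

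**Conclusion.** The concern holds. On the SAP's own inputs the unadjusted requirement is 36 per group (37 by t-test), so the stated 17 is about half of it. With ICC .03 and one school per arm, power for a 10-point difference is about 71% at 200 per school and cannot exceed about 78%. The statements that 200 per school is sufficient and that the sample is ample are both wrong as written.

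The result assumes a between-group comparison, SD 15, ICC .03, a two-sided test, and no variance reduction from baseline data. The claim about any school size needs an ICC above about .028; the error in the unadjusted number does not. How 17 arose is not known. The outcome affected is secondary, and the primary feasibility aim is untouched.

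**What to change.** In SAP section D:

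1. Replace 17 per group with 36 per group (37 by t-test), described as the requirement under the stated SD of 15. If the outcome is analysed as yes/no per student, re-derive the figure from an assumed baseline proportion and say what that assumption is.
2. Delete the statement that two schools of 200 give 80% power, and the sentence "Thus, our proposed sample will be more than adequate to evaluate study aims".
3. State that with one school per arm and ICC .03 the effective sample is at most about 33 per arm, so 80% power for a 10-point difference is unattainable at any enrolment. Add that one school per arm leaves no degrees of freedom for between-school variance.
4. Describe the behavioural outcomes as estimation only, and align the text on the planned chi-square tests, ANOVA and paired t-tests with that purpose, so that a non-significant result is not read as evidence of no effect.

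The cost is SAP wording only: no extra schools, students or data. The stated power becomes less favourable.
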